1. STUDY SYNOPSIS

Study Title	Comparison of the Effectiveness of Blood Flow Restriction Exercise and Eccentric Exercise in Patients Diagnosed with Lateral Epicondylitis
Study Design	Prospective, randomized controlled trial, three parallel groups
Study Site	Dokuz Eylul University, Department of Orthopedics and Traumatology, Izmir, Turkey
Study Population	Patients aged 18 years and older diagnosed with unilateral lateral epicondylitis
Sample Size	27 patients (9 per group)
Intervention Groups	Group 1: Blood flow restriction exercise (BFRE) + stretching + orthosis Group 2: Eccentric exercise + stretching + orthosis Group 3: Orthosis + stretching only
Treatment Duration	6 weeks
Primary Outcome	Pain intensity (Visual Analog Scale, 0-10 cm)
Secondary Outcomes	Hand grip strength (JAMAR dynamometer, kg) Pinch strength (Pinch meter, kg) Upper extremity function (DASH questionnaire, 0-100)
Assessment Time Points	Baseline and 6 weeks
Statistical Methods	Mixed model ANOVA, paired t-tests, one-way ANOVA
Ethics Approval	Dokuz Eylul University Non-Interventional Research Ethics Committee, No: 2021/28-31, Date: 13 October 2021
Enrollment Period	November 2021 – October 2024
Study Completion	October 2024

2. BACKGROUND AND RATIONALE

Lateral epicondylitis (tennis elbow) is a musculoskeletal disorder characterized by pain and tenderness at the lateral epicondyle of the elbow, affecting approximately 1–3% of the general population. The condition results from degenerative changes in the extensor carpi radialis brevis (ECRB) tendon caused by repetitive microtrauma.

Eccentric exercise has been widely recommended as a first-line conservative treatment. However, eccentric protocols typically require loading at 70% or more of one-repetition maximum (1-RM), which may not be tolerated by patients experiencing significant pain.

Blood flow restriction exercise (BFRE) is a training method involving the application of external pressure to the proximal limb using pneumatic cuffs, partially restricting arterial flow and completely restricting venous return during low-load resistance exercise (20–40% of 1-RM). BFRE has demonstrated effectiveness in various musculoskeletal conditions but evidence for lateral epicondylitis remains limited.

This study was designed to compare the effectiveness of BFRE with eccentric exercise and standard orthosis treatment in lateral epicondylitis.

3. STUDY OBJECTIVES AND HYPOTHESES

Primary Objective: To compare the effectiveness of BFRE, eccentric exercise, and orthosis use on pain reduction in patients with lateral epicondylitis.

Secondary Objectives: To compare the effects of the three interventions on hand grip strength, pinch strength, and upper extremity functional disability.

Hypotheses:

H0: There is no difference between BFRE, eccentric exercise, and orthosis groups in terms of functional level, pain, and grip strength.

H1: BFRE has a significant effect on functional level, pain, gross and fine grip strength in patients with lateral epicondylitis.

H2: Eccentric exercise has a significant effect on functional level, pain, gross and fine grip strength compared with BFRE in patients with lateral epicondylitis.

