11.8 Significance Level

The significance level was set at $p < 0.05$ for all analyses (two-tailed).

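### The null hypothesis spans function, pain and grip although VAS pain is the only primary outcome, so rejecting it on any one outcome at 0.05 carries an error of about 9–14%, not 5%

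*Combined protocol and SAP*

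**What the plan says.** The objectives in section 3 are ordered clearly. The primary one is "To compare the effectiveness of BFRE, eccentric exercise, and orthosis use on pain reduction in patients with lateral epicondylitis"; the secondary one is "To compare the effects of the three interventions on hand grip strength, pinch strength, and upper extremity functional disability". The synopsis and section 7.1 agree, naming VAS pain as the single primary outcome.

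The hypotheses in the same section do not follow that order:

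- H0: "H0: There is no difference between BFRE, eccentric exercise, and orthosis groups in terms of functional level, pain, and grip strength".
- H1: "H1: BFRE has a significant effect on functional level, pain, gross and fine grip strength in patients with lateral epicondylitis". No comparator is named.
- H2: "H2: Eccentric exercise has a significant effect on functional level, pain, gross and fine grip strength compared with BFRE in patients with lateral epicondylitis".

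Section 11.5 makes the time x group interaction the primary focus but names no outcome and refers to none of the three hypotheses. Section 11.7 allows pairwise comparisons after a significant ANOVA and names no adjustment. Section 11.8 states: "The significance level was set at $p < 0.05$ for all analyses (two-tailed"). No section gives a testing order, a multiplicity procedure or a rule for mixed results.

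**The concern.** A single primary outcome protects a trial's conclusion only if the hypothesis being decided depends on that outcome. Here it does not. H0 denies a difference in function, pain and grip together, so logically a difference in any one of them contradicts it. With each outcome tested at 0.05 and no stated rule, H0 can be rejected by three routes, of which VAS is only one.

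The practical risk is a report in which VAS shows no group difference, DASH or grip gives p < 0.05, and the trial is said to have rejected its null hypothesis. The plan as written permits that statement, and the 5% level in section 11.8 does not describe its error rate.

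**Working it through.** **The plan's own figure.** Section 8 gives an effect size of 1.8, alpha 0.05, power 95% and 9 per group. Reading 1.8 as a standardised difference between two groups (the metric is not named), two-sided:

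n = 2 × (1.960 + 1.645)² / 1.8² = 2 × 13.00 / 3.24 = 8.02, rounded up to 9 per group.

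The exact noncentral t power at 9 per group is 94.75%, so the stated size is reproduced to within rounding. It is based on one pain effect and one test at 0.05. The stated 5% belongs to that one test and not to a joint hypothesis.

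**Inputs for the error of H0.** Three groups of 9 (section 8); one interaction test per outcome at 0.05 (sections 11.5 and 11.8); three outcomes in H0 (section 3). With two time points, the time x group interaction is the same as a one-way ANOVA on the change score, F(2, 24). The correlation between outcomes is not in the documents, so a range is shown.

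**Independent outcomes.**

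- Three outcomes: 1 − 0.95³ = 14.3%.
- Four outcomes, if pinch is counted: 1 − 0.95⁴ = 18.5%.

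**Correlated outcomes.** These come from 100,000 simulated trials per setting, with no true effect and equally correlated normal change scores. The independent row uses the formula above.

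| Assumed correlation | Any of 3 significant | Any of 4 significant |
|---|---|---|
| 0 | 14.3% | 18.5% |
| 0.3 | 13.7% | 17.6% |
| 0.5 | 12.7% | 16.0% |
| 0.7 | 11.5% | 13.7% |
| 0.9 | 8.7% | 9.7% |

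The VAS test alone rejects in 5.0% of trials at every setting.

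**The harmful case.** The chance that DASH or grip is significant while VAS is not equals the any-of-three rate minus the VAS rate:

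- correlation 0: 14.3 − 5.0 = 9.3%
- correlation 0.5: 12.7 − 5.0 = 7.7%
- correlation 0.7: 11.5 − 5.0 = 6.5%
- correlation 0.9: 8.7 − 5.0 = 3.7%

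**H1 and H2.** If every one of the four outcomes must be significant, the rejection rate with no true effect is at most about 1.7% (at correlation 0.9). Inflation therefore arises only on the any-outcome reading. The four-outcome column is also only a guide for these two hypotheses, because it uses the three-arm test, whereas H2 is a two-arm contrast and H1 names no comparator.

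**Can the three-arm VAS test decide H2?** Suppose BFRE and eccentric exercise are identical and only orthosis differs, by 1.8 SD. The noncentrality is 27 × 1.8² × (1/3) × (2/3) = 19.44, and F(2, 24) at 0.05 is significant in about 97% of trials. H2 would be false in nearly all of those significant results, so it needs its own pairwise contrast.

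**The case against.** The strongest reply is that the plan already separates primary from secondary. Section 3 does so for the objectives, and the synopsis and section 7 for the outcomes. This stands: the VAS interaction test has a 5% error, and a reader who infers that the primary test itself is inflated goes further than the documents allow. What is missing is the link from that test to H0.

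A second reply is that H1 and H2 join their outcomes with "and". This also stands. A reader might infer that all three hypotheses have inflated error, but on the natural reading of H1 and H2 the error is below 5%. The plan does not exclude the looser reading, and no more than that can be said.

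A reader might also infer the opposite fault, that requiring all four outcomes means the trial would usually fail to support H1 or H2 even when every effect is real. The figures do not bear this out. At an assumed 80% power per three-arm interaction test, joint power is 41%, 55% and 60% at correlations 0, 0.5 and 0.7, so it falls below one half only when outcomes are close to unrelated. At 95% per outcome, the level that section 8 plans for pain, it is 82%, 85% and 87%.

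Last, H0's "grip strength" may be meant to include pinch, so H0 and the other two may cover the same outcomes. That is a fair reading, and it would move H0 to the four-outcome column.

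**Conclusion.** The point holds for H0. As written it is a global null over at least three outcomes, each tested at 0.05 with no decision rule, and its false-rejection rate is about 9–14% for correlations from 0.9 down to 0 (about 10–19% if pinch is included). This assumes no true effect, equal correlations, normal change scores and one interaction test per outcome. The paired t-tests of section 11.6 and the unadjusted pairwise tests of section 11.7 are not counted.

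For H1 and H2 the point is conditional on reading them as met by any one outcome. The 5% error of the VAS interaction test is not in question. This is more than missing detail, because the plan as written permits a conclusion about H0 that does not carry the stated error rate.

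**What to change.** 1. **Section 3, H0:** restate as no difference between the three groups in 6-week VAS change. State in section 11.5 that the VAS time x group interaction at 0.05 decides it.
2. **Section 3, H1 and H2:** restate each for VAS with a named pairwise contrast (eccentric versus BFRE for H2; BFRE versus a named comparator for H1). Test these only if the VAS interaction is significant, and say so in section 11.7.
3. **DASH, grip and pinch:** make them secondary hypotheses. Either apply Holm to their three interaction tests (smallest p against 0.05/3 = 0.0167, next against 0.025, last against 0.05) or label them exploratory. In both cases state that they cannot support the main conclusion when VAS is not significant. Amend section 11.8 accordingly.
4. **Labelling:** mark the change as a post-hoc clarification. Section 13 places the end of recruitment in October 2024 and the analyses in December 2024, and section 14 says the trial was not prospectively registered. The pre-existing choice of VAS as primary outcome supports the restatement, but the restatement should not be presented as pre-specified.

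The cost is wording in sections 3, 11.5, 11.7 and 11.8, with no new data. The downside is that some secondary p-values below 0.05 would no longer count as confirmatory.

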4. STUDY DESIGN

This study was designed as a prospective, three-arm, parallel-group, randomized controlled trial. Patients were randomly allocated to one of three treatment groups using block randomization. Assessments were performed at baseline (pre-treatment) and at the end of the 6-week intervention period (post-treatment).

5. STUDY POPULATION

5.1 Inclusion Criteria

1. Clinical diagnosis of lateral epicondylitis confirmed by an orthopedic surgeon
2. Age 18 years or older
3. Unilateral lateral epicondylitis
4. Signed written informed consent form

5.2 Exclusion Criteria

1. Bilateral lateral epicondylitis
2. Cervical radiculopathy
3. History of elbow, forearm, or wrist pathology (previous surgery, tendon rupture, fracture, osteoporosis, neurological involvement, nerve paralysis)
4. Physiotherapy within the preceding 6 weeks
5. Malignancy
6. Cardiac arrhythmia, pacemaker use, coagulation disorders, anticoagulant therapy, or history of deep vein thrombosis
7. Systemic or neurological disease
8. Peripheral vascular disease or endothelial dysfunction
9. Conditions associated with endothelial dysfunction (uncontrolled hypertension, cardiovascular disease, systemic inflammation, obesity, diabetes, atherosclerosis)
10. Active infection

6. INTERVENTIONS

6.1 Group 1 — Blood Flow Restriction Exercise (BFRE)

Arterial occlusion pressure (AOP) was individually determined using a pneumatic cuff and pulse oximetry (Zeng et al., 2019). Cuff pressure was gradually increased until the pulse and SpO₂ waveform disappeared on the pulse oximeter, which was recorded as AOP.

Exercise was performed at 30% of individually determined AOP. A sphygmomanometer cuff was applied to the proximal upper arm. Pressure was maintained throughout exercise sets and rest intervals. Exercise load was set at 30% of 1-RM.

Protocol: 3 sets x 15 repetitions, 1-minute rest between sets, twice weekly for 6 weeks.

Stretching: 3 repetitions x 30 seconds before and after each session (45-second rest between stretches).

Non-exercise days: Home stretching program 2 times/day, 3 repetitions x 30 seconds.

Orthosis: Wrist extension orthosis (15–20 degrees) worn throughout the study.

6.2 Group 2 — Eccentric Exercise

Slow eccentric wrist extensor exercises were performed with the elbow in full extension and forearm in pronation. From a wrist extension position, the weight was slowly lowered into flexion over approximately 30 seconds.

Protocol: 3 sets x 10 repetitions, 1-minute rest between sets, five times weekly for 6 weeks, at 70% of 1-RM.

Stretching and orthosis protocols were identical to Group 1.

Non-exercise days: Home stretching program 2 times/day, 3 repetitions x 30 seconds.

6.3 Group 3 — Orthosis (Reference Standard Conservative Treatment)

Participants wore a wrist extension orthosis maintaining 15–20 degrees of extension throughout the day, removing it only during sleep, bathing, and stretching exercises.

Stretching: Home stretching program 2 times/day, 3 repetitions x 30 seconds.

6.4 Exercise Progression

Exercise protocols were kept constant throughout the 6-week period without progression. This decision was based on: (1) the risk of exacerbating tendon symptoms with rapid progression; (2) ensuring standardized comparison across groups; (3) allowing sufficient time for tendon adaptation; and (4) improving patient compliance by reducing protocol complexity.

6.5 Stretching Protocol (All Groups)

Shoulder at 90 degrees flexion, elbow in full extension, forearm in pronation, wrist in flexion and ulnar deviation. The contralateral hand was used to apply a sustained stretch for 30 seconds, repeated 3 times with 45-second rest intervals.

7. OUTCOME MEASURES

7.1 Primary Outcome

Visual Analog Scale (VAS): A 10-cm horizontal line where 0 = no pain and 10 = worst imaginable pain. Patients marked their current pain level. Assessed at baseline and 6 weeks.

7.2 Secondary Outcomes

Hand Grip Strength: Measured using a JAMAR hydraulic hand dynamometer (kg). Standardized position: elbow at 90 degrees flexion, forearm in neutral. Mean of 3 consecutive trials recorded.

Pinch Strength: Measured using a pinch meter (kg). Three pinch types assessed: lateral, palmar, and tip-to-tip. Mean of 3 trials across all types recorded.

DASH Questionnaire: Disabilities of the Arm, Shoulder and Hand. 30-item self-report questionnaire scored 0 (no disability) to 100 (maximum disability). Turkish validated version used.

8. SAMPLE SIZE CALCULATION

Sample size was calculated using G*Power software (version 3.1.9.4, Faul et al., 2007).

Parameters: Effect size = 1.8 (based on previously reported pain reduction rates in lateral epicondylitis exercise studies); Type I error rate $\alpha = 0.05$; Statistical power = 95% ($1 - \beta = 0.95$).

Result: Minimum 9 participants per group, total N = 27.

9. RANDOMIZATION

Participants were allocated using block randomization with blocks of nine. Each block contained three assignments for each group (BFRE, Eccentric, Orthosis), ensuring equal distribution. Randomization was performed by a researcher not involved in patient assessment or treatment delivery.

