10. DATA COLLECTION PROCEDURES

All outcome measures were assessed by the same examiner at two time points: baseline (before initiation of treatment) and at the end of the 6-week intervention period.

JAMAR dynamometer and pinch meter measurements were performed according to the American Society of Hand Therapists (ASHT) standardized protocols. Three consecutive measurements were recorded for each strength test, with 30-second rest intervals between trials.

Home exercise adherence was monitored using exercise diaries. Patients recorded the date, number of sets and repetitions, and pain level for each session. Diaries were reviewed during weekly clinical sessions.

For the BFRE group, SpO₂ monitoring was performed throughout each session for safety.

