14. LIMITATIONS

1. Small sample size ($n = 9$ per group) limiting statistical power and generalizability.
2. Single-center study design limiting external validity.
3. Open-label design (no blinding of patients or therapist).
4. Short-term follow-up (6 weeks only, no long-term data).
5. No exercise progression applied during the 6-week protocol.
6. AOP determined by pulse oximetry rather than Doppler ultrasonography.
7. The trial was not prospectively registered in a clinical trial registry.

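### Fixed blocks of nine at one open-label center, with no concealment method described, make late-block allocations predictable to anyone who knows the block size, while two loosely worded exclusions leave room for judgement at enrolment

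*Combined protocol and SAP*

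**What the plan says.** Section 9 (Randomization) gives a single block size: "Participants were allocated using block randomization with blocks of nine". It continues: "Each block contained three assignments for each group (BFRE, Eccentric, Orthosis), ensuring equal distribution". On who did it, the section says: "Randomization was performed by a researcher not involved in patient assessment or treatment delivery". It does not say who enrolled patients, how the sequence was concealed, whether the block size was withheld, or whether eligibility was confirmed before an allocation was requested.

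Section 14 (Limitations) lists "Single-center study design limiting external validity" and "Open-label design (no blinding of patients or therapist". Section 10 adds: "All outcome measures were assessed by the same examiner at two time points".

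The exclusions in section 5.2 apply to all arms alike. Item 7 is "Systemic or neurological disease". Item 9 is "Conditions associated with endothelial dysfunction (uncontrolled hypertension, cardiovascular disease, systemic inflammation, obesity, diabetes, atherosclerosis". Neither item defines its terms, and obesity has no measurable limit.

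**The concern.** Selection bias at enrolment needs two things: some ability to foresee the next assignment, and some discretion over who is admitted. The plan leaves an opening for both.

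*Foresight.* With one center there is one sequence. The three regimens in section 6 (cuff sessions, loaded eccentric sessions, orthosis with stretching) cannot be mistaken for one another once treatment starts. If every block is nine with three per arm, a person who counts past assignments can tell when an arm has no places left. A separate researcher holding the list does not prevent this, because the inference comes from assignments already visible.

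*Discretion.* Item 9 names hypertension only when uncontrolled, a qualifier that serves a purpose only if controlled hypertension is admissible. Yet systemic disease in item 7, or cardiovascular disease in item 9 itself, can be read to cover the same patient. Obesity is left to judgement. Several of these exclusions plausibly matter most for the cuff arm, so a borderline case might be judged differently once BFRE is known to be unavailable.

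With nine patients per arm, one or two such decisions would concern 1/9 = 11% to 2/9 = 22% of a group.

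**Working it through.** **Inputs.** Block size 9, three per arm (section 9); N = 27, 9 per group (section 8); one center, patients and therapist unblinded (section 14). Assumption not in the documents: the recruiter knows the block size and all earlier assignments. All figures below depend on it.

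**The plan's own figure.** 27 / 9 = 3 complete blocks and 3 × 3 = 9 per arm, which agrees with section 8. No figure in the plan is disputed here.

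**Places that open after BFRE is exhausted.** In a block, the 6 non-BFRE places fall at random into the 4 gaps around the 3 BFRE places. The expected number after the last BFRE place is 6/4 = 1.5.

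As a check by position, the chance that BFRE is exhausted before place j is C(j−1, 3)/C(9, 3), where C(9, 3) = 84. For places 4 to 9 this gives 1/84, 4/84, 10/84, 20/84, 35/84 and 56/84 (1.2%, 4.8%, 11.9%, 23.8%, 41.7%, 66.7%). The sum is 126/84 = 1.5.

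Over three blocks: 3 × 1.5 = 4.5 of 27 = 17%. A block has at least one such place with probability 2/3, so a three-block trial does with probability 1 − (1/3)³ = 96.3%.

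**Places that are fully determined.** A place is determined when only one arm remains, so the count equals the length of the final run of one arm: 1 + 2/8 + (2/8)(1/7) = 1.286 per block. Over three blocks: 3.86 of 27 = 14%.

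**Best guess.** The rule is to guess the arm with most places left and to split ties at random. Enumerating all 1680 orderings of a 3-3-3 block gives 4.787 correct per block. Over three blocks that is 14.4 of 27 = 53%, against 9 of 27 = 33% by chance.

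**Alternatives.** For one 9-9-9 list, the 18 non-BFRE places fall into 10 gaps, so 18/10 = 1.8 places follow the last BFRE place.

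| Scheme | BFRE exhausted, of 27 | Determined, of 27 | Correct guesses |
|---|---|---|---|
| Fixed blocks of 3 | 9.0 (33%) | 9.0 (33%) | 16.5/27 = 61% |
| Fixed blocks of 6 (scaled to 27) | 6.0 (22%) | 5.4 (20%) | 15.15/27 = 56% |
| Fixed blocks of 9 (the plan) | 4.5 (17%) | 3.9 (14%) | 53% |
| One list of 27 | 1.8 (7%) | 1.4 (5%) | 46% |

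Among these schemes, smaller fixed blocks are worse than the plan's and a single list is better.

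**From predictability to patients.** An exhausted place matters only if a borderline candidate fills it. The documents give no share of such candidates. Assuming 5% to 30%, 4.5 × 0.05 = 0.2 to 4.5 × 0.30 = 1.4 patients in the whole trial.

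**The case against.** The strongest reply is that the chain from block size to bias is conditional at every link. Section 14 describes the patients and therapist as unblinded and does not mention the recruiter. Nothing says that the recruiter knew the block size or kept a tally. A researcher outside assessment and treatment did the randomization, and nine is already a less predictable fixed size than three or six. Section 11.4 plans baseline comparisons across arms. All of this stands, and it is why the figures are upper limits. It does not close the gap: separation from enrolment is not stated, no concealment is described, and section 11.4 does not name BMI or comorbidity.

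Three stronger readings are tempting, and the documents do not support them.

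- *That the exclusions contradict each other.* Every item in section 5.2 is an exclusion. Meeting any one keeps a patient out, and no item can admit a patient whom another excludes. The fault is unclear wording, not contradiction.
- *That borderline patients were steered into the eccentric and orthosis arms.* The documents contain no evidence of selective admission.
- *That any such steering would favor BFRE.* Nothing in the documents links controlled hypertension or obesity to a poorer six-week change in pain, strength or DASH. The primary test is the time by group interaction (section 11.5), so a baseline imbalance does not translate directly into a treatment effect.

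It is also true that recruitment ended in October 2024, so changes to the list or criteria cannot help this trial.

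**Conclusion.** The point holds as a weakness in the allocation procedure and its description, not as a finding of bias. For a recruiter who knows the block size and counts, the plan's scheme leaves an average of 4.5 of 27 places with BFRE known to be exhausted, 3.9 of 27 fully determined, and a 53% success rate in guessing the next arm. Without that knowledge, predictability is lower by an amount the documents do not allow one to calculate.

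The unclear status of controlled hypertension and the undefined obesity criterion leave room for judgement that a foreseen allocation could influence. Whether that happened, and in which direction, cannot be determined from the documents. A less predictable list with the same 9/9/9 totals was available at little cost.

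**What to change.** **Section 9, for this design or its reuse.** Replace the fixed blocks of nine with one permuted list of 27, nine per arm. This lowers BFRE-exhausted places from 4.5 to 1.8, a reduction of 2.7/4.5 = 60%, and correct guesses from 53% to 46%. Alternatively, use varied block sizes withheld from recruiters; this mainly removes certainty about the next arm and does little for the guess rate. Do not simply shorten the fixed block. Require a signed eligibility form before allocation is requested.

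**Section 5.2.** Reconcile items 7 and 9 so that each patient, including one with controlled hypertension, gets a single answer before allocation, and make the obesity criterion measurable. The content of those criteria is for the investigators to decide.

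**For the completed trial.** State who enrolled patients, how the sequence was concealed and whether the block size was known. Tabulate BMI, hypertension and comorbidity by arm where recorded. Repeat the primary analysis without allocations made after BFRE was exhausted in the block, labelled exploratory. On average this removes 4.5/2 = 2.25 patients from each of the other two arms, leaving about 9 versus 6.75 and 6.75, so it will be imprecise.

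**Cost.** A different random list, one form and two reworded items; for the completed trial, one table and one extra analysis. The drawback of a single list is looser balance over the three-year enrolment period, though the final group sizes stay 9/9/9.
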